5.6.2 Analgesics use

Pain palliation resulting from antitumor therapy provides direct evidence of treatment benefit when combined with evidence of antitumor activity ([R17-3501](#)). Intensification of pain palliation will be defined as a ≥ 2 -point increase in the 8-point Analgesic Quantification Algorithm (AQA, see [Table 5.6.2: 1](#)). AQA is a modification of the World Health Organization Analgesic Treatment Ladder that includes additional specificity for patients receiving strong opioids. This algorithm facilitates differentiation between the full ranges of doses of strong opioids used by patients and thus, more accurately enables researchers to determine and control for changes in levels of analgesic medication use over time in clinical trials ([R17-2771](#)). It will be completed by the investigator at the same visits as the PROs.

Table 5.6.2: 1 AQA

AQA score	Description
0	No analgesic
1	Non-opioid analgesics
2	Weak opioids
3	Strong opioids ≤75 mg OME per day
4	Strong opioids >75–150 mg OME per day
5	Strong opioids >150–300 mg OME per day
6	Strong opioids >300–600 mg OME per day
7	Strong opioids >600 mg OME per day

5.6.3 Health care resource utilisation

Health care resource utilisation (HCRU) data will allow calculation of direct and indirect costs and will be used for health economic analysis (i.e. cost-effectiveness analysis).

Resource use will be captured at the time points specified in the [Flow Chart](#). Information on caregiver support (home care), general practitioner, outpatient and hospital visits (other than scheduled visits) will be collected in the CRF and as part of AE reporting to inform on healthcare resource use required to treat the trial indication and adverse events observed during the trial.

5.7 APPROPRIATENESS OF MEASUREMENTS

All clinical assessments are standard measurements commonly used in studies of advanced solid tumours. RECIST version 1.1 is used for assessment of the change in tumour burden. These criteria are well established and well received by the regulatory authorities and scientific community.

The NCI CTCAE criteria are used in the assessment of AEs in cancer patients. In the present trial CTCAE version 5.0 ([R18-1357](#)) will be used.

The questionnaires used in the present trial have been validated and address the outcome to be evaluated (i.e. symptoms or HRQOL). The BPI-SF has been accepted by multiple national authorities including FDA and EMA, and the NRSBI-16 and the PRO-CTCAE have been developed in accordance with FDA guidance for patient-reported outcome measures.

6 INVESTIGATIONAL PLAN

6.1 VISIT SCHEDULE

The visit schedule is in detail described in the [Flow Chart](#) for all patients randomised to either the treatment with xentuzumab in combination with everolimus and exemestane or to placebo in combination with everolimus and exemestane. Unscheduled visits can be performed as necessary and assessments will be performed as required at the discretion of the investigator.

6.2 DETAILS OF TRIAL PROCEDURES AT SELECTED VISITS

See the [Flow Chart](#) and [Section 5](#) for details on the procedures performed at each visit. Per Protocol version 6, reference the revised and reduced flow chart and section 5 as appropriate.

6.2.1 Screening

Screening Period

All patients will need to sign the informed consent form (ICF). Only patients who have tested positive for HR and negative for HER2 by prior local analysis according to ASCO/CAP guidelines ([R15-6055](#), [R17-4255](#)) are eligible for the trial. Archival tumour tissue sample must be submitted to the central laboratory to retrospectively confirm HR/HER2 status (see [Section 5.4](#)). If archival tissue is not available, provision of detailed information from the original histology report may be agreed with the sponsor on a case by case basis. In the case that prior information regarding the patient's genomic breast cancer signature is available, an anonymised copy of the report will be collected for the trial database and specified parameters will also be recorded in the CRF.

Demographic information (sex, date or year of birth (in accordance with local laws and regulations), race) will be obtained, based on information in the patients' medical records. Examinations and assessments per [Flow Chart](#) will be conducted and patients' medical history will be collected. Inclusion and exclusion criteria must be assessed (see [Sections 3.3.2](#) and [3.3.3](#)). Baseline images must be available as outlined in the [Flow Chart](#).

Concomitant diagnoses and/or therapies present during trial participation (between first ICF and the first follow-up visit) will be recorded in the CRF. Medical history of mBC will be obtained and reported in the CRF:

- The date of first histological diagnosis
- The primary tumour site
- The number and location of metastatic sites (e.g. bone, lymph nodes, skin, subcutaneous, soft-tissue, (contralateral) breast and combinations thereof)
- Tumour stage according to the TNM-classification at diagnosis
- Previous treatment for mBC, including any surgery, radiotherapy, and/or systemic therapy, including start and end dates and the outcome.

Re-screening will be allowed once. Re-screened patients will receive a new

patient number. In case of re-screening any procedures that fall outside the required screening window as defined in [Flow Chart](#) must be repeated.

6.2.2 Treatment period

Treatment visits are specified in the [Flow Chart](#) and must be conducted as scheduled and outlined there. Treatment cycles are 4 weeks (28 days) in duration until treatment week 80 and then 8 weeks (56 days) in duration.

All planned visit dates are calculated from the start of day 1 (visit 1) of cycle 1. If a visit is missed there will be no re-scheduling; if a patient is required to attend the study site between the “missed” and next scheduled visit, then the missed visit assessments should be performed. The current date and the reason for the delay must be noted in the medical records. All subsequent visits must adhere to the scheduled programme of visits for all cycles of treatment.

Imaging visits must adhere to the schedule provided in the [Flow Chart](#) at all times, unless they are scheduled for suspected PD.

6.2.2.1 End of treatment visit and follow-up visit 1

The EOT visit will be performed as soon as possible (within 14 days) after permanent discontinuation of **all** trial medications for any reason or as soon as possible after the investigator became aware that the trial medication had been terminated. Investigators must ensure that PK, ADA and nAB samples are taken as described in the [Flow Chart](#), [Section 5.3](#) and [Appendix 10.1](#).

The follow-up Visit 1 (EOR/FU1) will be performed 42 (+7) days after permanent discontinuation of all trial medications and is primarily to collect follow-up safety information as required by regulatory authorities. For the majority of patients, progression will already be documented at this point.

6.2.2.2 Treatment beyond progression

In case of continued clinical benefit judged by the investigator and based on careful clinical assessment, patients may be allowed to continue trial medications beyond disease progression as defined by RECIST 1.1 criteria. Clinical benefit can include, but will not be restricted to, significant symptom control of originally symptomatic tumours. Patients who continue as described will continue to follow the trial schedule for treatment visits (see [Flow Chart](#)) including the imaging and clinical tumour evaluations. Trial medication may be continued as long as judged beneficial by the investigator.

6.2.3 Follow up period and trial completion

Not applicable as per CTP version 6. The end of study is defined as EOR/FUP1

6.2.3.1 Extended follow-up period

For patients without objective disease progression and who have not started a new anti-cancer therapy prior to FU1, additional follow-up visits for progression will be performed every 56 days (8 weeks) \pm 7 days after the EOT visit for patients who did not yet start cycle 20 and every 16 weeks (112 days) for patients who started cycle 20. The follow-up for progression period will end at the earliest if one of the following events is met:

- Lost to follow-up
- Disease progression
- Start of a new anti-cancer therapy
- Death
- End of whole trial as specified in [Section 8.6](#)

The following will be obtained and/or performed during the follow-up visits for progression.

- For each drug-related SAE/AESI, the investigator should provide the information with regard to concomitant medication and the medication administered to treat the adverse events on the appropriate CRF pages and the SAE form including trade name, indication and dates of administration
- Record performance status (ECOG)
- Quality of life questionnaires
- Perform tumour assessment and imaging
- Treatment and start date of any subsequent anti-cancer therapy including the name and type of the anti-cancer drug and/or best supportive care (if applicable)
- Outcome (in case the patient had PD the actual date of PD shall be recorded, date of and reason for death, if applicable)
- Results from pregnancy testing (if applicable) see [Flowchart](#)

6.2.3.2 Follow-up for Overall Survival

All patients will be followed up for overall survival at 84 day (12 weeks) intervals until

- Death
- Lost to follow-up or
- Completion of the whole trial (as specified in [Section 8.6](#))

These visits may also be performed by e.g. telephone interview or via written correspondence in case the patient is unable to visit the investigator. The following information will be collected during the follow-up for survival period:

- Date and type of contact
- Post progression information including further anti-cancer treatment: regimen and drug name, start and stop dates, response to further anti-cancer treatment if available
- For each drug-related SAE/AESI, the investigator should provide the information with regard to concomitant medication and the medication administered to treat the

AEs on the appropriate CRF pages and the SAE form including trade name, indication and dates of administration

- Outcome event (record date of and reason for death, if applicable)
- Results from pregnancy testing (if applicable) see [Flowchart](#)

6.2.3.3 Trial completion for an individual patient

A patient is considered to have completed the trial in case any of the following applies:

- Completion of planned follow-up periods
- Lost to follow-up
- Refusal to be followed-up
- Death

If a patient cannot be contacted for vital status, information may also be obtained by other means, e.g. contact with patients' health care providers, public sources, e.g. death registry, obituary listing, etc. when it is available and verifiable.

7 STATISTICAL METHODS AND DETERMINATION OF SAMPLE SIZE

7.1 STATISTICAL DESIGN - MODEL

This is a randomised, double-blind, placebo-controlled multi-centre trial in women with HR+/HER2- advanced or metastatic breast cancer with non-visceral disease. The primary objective of the trial is to evaluate whether xentuzumab in combination with everolimus and exemestane prolongs PFS, independently assessed according to RECIST 1.1, in comparison to everolimus and exemestane alone.

Based upon these design considerations, treatment groups will be compared for the primary endpoint via a stratified log-rank test, stratified by the presence of baseline bone-only metastases (Yes/No), prior CDK4/6 inhibitor treatment (Yes/No) and menopause status (pre/post).

If the criterion for the seamless option is met then this Phase II trial will be expanded into a confirmatory Phase III trial, similar to the 2-in-1 design outlined in [R18-2061](#). Pertinent detail regarding hypothesis testing, alpha-spending/control along with increases in sample size in the expansion scenario has been detailed in the following sections. However, prior to expanding the trial additional detail will be provided via a formal protocol amendment.

7.2 NULL AND ALTERNATIVE HYPOTHESES

If at the time-point of the primary PFS analysis for this Phase II trial the hazard ratio (using the model defined in [Section 7.3.1](#)) is below a pre-defined criterion (to be defined in the DMC charter, prior to trial initiation), in favour of the xentuzumab arm, then the trial will be expanded into a confirmatory Phase III trial. No formal hypothesis testing will be performed if the trial is not expanded.

However, if the trial is expanded, formally, the null hypothesis for the primary PFS endpoint at the end of Phase III is:

$$H_0: S_{PFS; xentuzumab}(t) \leq S_{PFS; control}(t), \text{ for all } t > 0,$$

versus the alternative hypothesis:

$$H_1: S_{PFS; xentuzumab}(t) > S_{PFS; control}(t), \text{ for any } t > 0,$$

where $S_{PFS}(t)$ is the probability that a patient passes time t without experiencing a PFS event.

The expanded study will be considered positive if the null hypothesis for the primary endpoint can be rejected.

Also in the expanded trial scenario, for the secondary OS endpoint, the null hypothesis is:

$$H_0: S_{OS; xentuzumab}(t) \leq S_{OS; control}(t), \text{ for all } t > 0,$$

versus the alternative hypothesis:

$$H_1: S_{OS; xentuzumab}(t) > S_{OS; control}(t), \text{ for any } t > 0,$$

where $S_{os}(t)$ is the probability that a patient passes time t without experiencing an OS event.

The hypothesis testing will be performed on all randomised patients. The testing strategy includes the endpoints PFS and OS, tested in a hierarchical manner, and will control the overall type-1 error rate at a level of 0.025 (one-sided).

If the trial is expanded then the primary PFS analysis at the end of Phase II will be considered as an interim analysis. Refer to [Section 7.4](#) for further details on this planned interim analysis and the control of the type I error rate in the situation where the trial is expanded.

Superiority, for the endpoint of interest will be declared if the related null hypothesis is rejected in favour of the alternative at the defined significance level and the estimated hazard ratio of xentuzumab vs. control is <1 .

The primary objective of this Phase II trial, that xentuzumab in combination with everolimus and exemestane prolongs PFS, will be addressed by assessing whether or not the criterion for the seamless option has been met. If the seamless option is not met, the observed results will be evaluated in an explorative manner to see if they are sufficient for further development of this compound in this indication (e.g. via a separate Phase III trial). If the seamless option is met then expansion into a Phase III trial will allow for formal hypothesis testing via a one-sided test at an alpha level determined by a number of factors (refer to [Section 7.4](#)), controlling for the overall type I error rate of 0.025 (one-sided). The hypothesis testing will be supported by the hazard ratio and corresponding 95% CI from a stratified Cox proportional hazards model to describe the magnitude and precision of treatment effects.

7.3 PLANNED ANALYSES

The primary analysis of PFS for this Phase II trial will take place when approximately 40 patients have had disease progression (assessed by independent review) or died. The time point of reaching 40 events will be estimated using investigator assessed events and the discrepancy rates observed between independent and investigator data during the trial. The estimation of this time point is likely to lead to some deviation, though relatively small, from the planned 40 independent assessed events. Based on assumed median PFS times (refer to [Section 7.7](#)), the analysis is expected to take place 15 months after the last patient has been randomised. This analysis will be performed by the DMC.

If the criterion for the seamless option is met then the trial will be expanded into a confirmatory Phase III trial and remain double-blind. If the criterion is not met then the database will be unblinded and a clinical trial report (CTR) written, including the evaluations of the primary, secondary and further endpoints. Note that based on these results it is still possible that clinical development in this indication will be continued (e.g. via a separate Phase III trial), in addition patients randomised into this Phase II trial will have further data collected and reported upon, beyond the unblinding time-point. Blinded dummy treatment group assignments will be used in the study database whilst the trial remains blinded. [Section 4.1.6](#) provides further details on the blinding and procedures for unblinding.

An exception to the above plan will occur if the proportion of randomised patients dropping out of the trial without evidence of disease progression, becomes so high that reaching 40 PFS events is either not possible, or has not been met 20 months after the last patient has been randomised. In such an unlikely scenario no DMC analysis will be performed and therefore

the criterion for seamless expansion will not have been met. In this situation the database will be unblinded and a CTR written, including the evaluations of the primary, secondary and further endpoints.

Imaging related endpoints will be both independently assessed and investigator assessed according to RECIST 1.1. The data from the independent assessments will be considered primary, with investigator assessment data as supportive.

The primary efficacy analyses will be performed on the randomised set (RS), consisting of all randomised patients. Patients randomised and not treated will be analysed according to the censoring rules defined in [Section 7.5](#). Randomised patients who receive the wrong treatment will be analysed according to their planned randomised treatment group. No per-protocol analysis is planned.

Stratification (where stated) of analyses will be based on the presence of baseline bone-only metastases (Yes/No), prior CDK4/6 inhibitor treatment (Yes/No) and menopause status (pre/post). Refer to [Section 7.6](#) for further details on the randomisation stratification factors.

The safety analysis will be based on the treated set (TS), consisting of all patients treated with at least one dose of any study treatment. Patients will be analysed according to the actual treatment received.

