5. ASSESSMENTS

5.1 ASSESSMENT OF EFFICACY

Response and progression will be evaluated in this trial using RECIST guideline (version 1.1) in combination with MD Anderson criteria for patients with target and/or non target bone lesions, at the time points specified in the [Flow Chart](#). Adaptions to the MD Anderson criteria include clarifications and modifications to the published criteria and aim to provide more objective and reproducible assessments for the disease under study. A modification to the RECIST 1.1 criteria in regards to target lesion location selection will also be also implemented to properly address the patient population being studied ([R17-4024](#)). See [Appendix 10.4](#) for details on lesion measurements and response assessment.

Tumour response will be assessed by the investigator and central independent review throughout the trial. Clinical decisions will be based on investigator assessment of tumour response. The results of the independent assessment will not be communicated to the investigator. Instruction for obtaining images and the shipment/transfer of image data will be provided by the central image review provider.

As of 29 September 2021, tumor assessments will be assessed per local practice. Only the overall response will be collected in the eCRF.

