7.7 DETERMINATION OF SAMPLE SIZE

For the primary endpoint of PFS, it is assumed that xentuzumab in combination with everolimus and exemestane will increase the median from 9.9 months ([R16-0802](#)) in the everolimus and exemestane alone group to 19.8 months. Assuming an exponential distribution, this is equivalent to a reduction in the risk for progression of disease or death of 50%, corresponding to an underlying hazard ratio (HR) of 0.50. With 80 eligible patients randomised over a 15 month period, 40 PFS events are predicted to be reached on average around 30 months after the first patient is randomised. This assumes approximately 20% of patients randomised will either drop out of the trial without evidence of disease progression or be assessed as non-PD by independent assessment when the investigator assigned disease progression. If this proportion differs significantly from the 20% assumed then the number of patients randomised may be increased in order to observe 40 PFS events in a timely manner, but the number of patients randomised will not exceed 100 patients.

[Table 7.7: 1](#) shows the probability of observing various HR thresholds for different underlying (true) HR values and accrued PFS events.

Table 7.7: 1 Probability (%) of observed HR for a range of underlying HRs and PFS event numbers

PFS Events	Underlying (True) HR	Probability ¹ observing HR			
		≤0.50	≤0.60	≤0.75	>0.75
50	HR=1.00	0.7%	3.5%	15.5%	84.5%
40		1.4%	5.3%	18.1%	81.9%
30		2.9%	8.1%	21.5%	78.5%
50	HR=0.60	26.0%	50.0%	78.5%	21.5%
40		28.2%	50.0%	76.0%	24.0%
30		30.9%	50.0%	72.9%	27.1%
50	HR=0.50	50.0%	74.0%	92.4%	7.6%
40		50.0%	71.8%	90.0%	10.0%
30		50.0%	69.1%	86.7%	13.3%
50	HR=0.40	78.5%	92.4%	98.7%	1.3%
40		76.0%	90.0%	97.7%	2.3%
30		72.9%	86.7%	95.7%	4.3%

¹ Calculated using the approximate normal distribution of the estimated log HR

With 40 PFS events, if the underlying HR is 0.50, the chance of observing a treatment effect with HR of ≤0.60 is 71.8%, while the chance of observing a treatment effect with HR of ≤0.75 is 90.0%. Also, if the underlying HR is 1.0, the chance of observing a treatment effect with HR of ≤0.60 is 5.3%, while the chance of observing a treatment effect with HR of ≤0.75 is 18.1%. If the PFS events were increased from 40 to 50, the probability of observing a treatment effect with HR of ≤0.60 is increased by 2.2% (from 71.8% to 74.0%) for an underlying HR of 0.50, similarly for a treatment effect with HR of ≤0.75 the increase in probability is 2.4%.

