
Probabilities of 71.8 or 90%, respectively, based on 40 PFS events and an underlying HR of 0.50 is considered high enough to provide evidence that will allow an informed decision to be made in terms of the next stages of development.

The trial includes a seamless option for the expansion of the ongoing Phase II trial into a Phase III trial provided the predefined criterion (to be defined in the DMC charter) is met after 40 PFS events have been observed.

If the trial meets the criterion for expansion a further 220 patients will be randomised, so 300 patients in total, 150 per treatment arm. Primary analysis would be planned after approximately 176 PFS events, 40 from the primary Phase II analysis time-point plus an additional 136 events after this time-point. With 220 additional patients randomised into the expansion part at a constant rate over a 14 month period, 176 PFS events are predicted to be reached on average around 64 months after the first patient is randomised into the Phase II trial. This includes a 4-month gap between the Phase II results and starting the expanded trial. It is expected that approximately 20% of patients randomised will either drop out of the trial without evidence of disease progression or be assessed as non-PD by independent assessment when the investigator assigned disease progression. This has been accounted for with the planned total of 300 patients to be randomised. Note as for the Phase II part if the drop-out rate differs significantly from 20% the total number of patients randomised may need to be increased from 300, but will not exceed 375.

The patient numbers have been chosen to provide a sufficient amount of efficacy and safety data for submission. A standalone Phase III trial, with an assumed HR of 0.60 and 176 events, would achieve an overall power of at least 90% controlling the overall type I error at 2.5% (one-sided). Also, when considering solely the expansion part with 136 events it is ensured that based on an assumed HR for the expansion part of 0.60 the respective one-sided (second stage) p-value would be less than 0.05 in 90% of the cases. Thereby it is assumed that the event size for the second stage is sufficiently large to allow for informed decision making on homogeneity across the two trial parts in the case of the seamless option being met.

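### Does the rule that cancels the DMC look (Protocol 7.3) need the loss measure of 7.7 and a tolerance around 40 events?

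*Protocol*

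**What the plan says.** **Default rule (Protocol 7.3).** The Phase II PFS analysis "will take place when approximately 40 patients have had disease progression (assessed by independent review) or died". Its date is projected from investigator-assessed events and the observed discrepancy rate, which is "likely to lead to some deviation, though relatively small, from the planned 40 independent assessed events". Sections 3.1 and 7.4 also say approximately 40.

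**Exception (Protocol 7.3).** It applies "if the proportion of randomised patients dropping out of the trial without evidence of disease progression, becomes so high that reaching 40 PFS events" is not possible, or has not been achieved 20 months after the last patient is randomised. "In such an unlikely scenario no DMC analysis will be performed and therefore" the expansion criterion counts as not met. The database is then unblinded and all endpoints are reported.

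**Planned loss (Protocol 7.7).** About 20% of patients "will either drop out of the trial without evidence of disease progression or be assessed as non-PD by independent assessment when the investigator assigned" progression. "If this proportion differs significantly from the 20% assumed then the number of patients randomised may be increased", up to 100. For the expanded trial the same section calls this combined figure a drop-out rate: "Note as for the Phase II part if the drop-out rate differs significantly from 20% the total number of patients randomised" may have to rise.

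The SAP covers only the case in which the trial is not expanded (Section 3) and does not mention the exception.

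**The concern.** Two features of the exception do not match the rest of the plan.

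- **Loss measure.** The exception repeats only the first of the two loss sources in Section 7.7. Central non-confirmation can remove events in much the same way. "Clinical decisions will be based on investigator assessment of tumour response" (Section 5.1), so a patient judged progressed at the site may start new therapy. Imaging then stops, and Table 7.5: 1 censors the patient. Taken literally, a shortfall from dropout ends in no DMC look, while an equal shortfall from central non-confirmation means waiting with no stated limit.
- **Event count.** The default tolerates a small deviation from 40, and the exception does not mention one. A count of 36 to 39 at the limit could be read as close enough under the default or as a failure under the exception.

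At stake is whether the DMC compares the hazard ratio with its charter criterion at all. Once the look is cancelled and the database unblinded, seamless expansion cannot be recovered.

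**Working it through.** **Inputs (Protocol 7.3, 7.6 and 7.7).** 80 patients, at most 100; 1:1 allocation; 15-month accrual; median PFS 9.9 months on control and 19.8 on xentuzumab (hazard ratio 0.50); 20% loss; limit 20 months after last randomisation, so month 15 + 20 = 35.

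**Assumptions.** Uniform accrual, still over 15 months when N = 100. Lost patients from either source never give an event.

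**1. The plan's own figures.** Table 7.7: 1 follows from P = Φ[(ln h − ln HR)·√d/2]. With d = 40, true HR 0.50 and h = 0.60: Φ[ln(0.60/0.50)·√40/2] = 71.8%. With h = 0.75 it is 90.0%. Both match. For timing, uniform accrual with 20% loss gives 42.3 events at month 30 and the 40th at month 27.8. A linear ramp in accrual gives 39.9 events at month 30, which agrees with the stated figure of about 30 months.

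**2. Event probability by month 35.** With λ = ln 2/median, accrual A = 15 and T = 35:

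p = 1 − [exp(−λ(T−A)) − exp(−λT)]/(λA)

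This gives 0.847 on control and 0.614 on xentuzumab. Without loss, expected events are 40 × (0.847 + 0.614) = 58.4 at N = 80, and 73.1 at N = 100.

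**3. How often the limit is missed.** The total is the sum of two binomials, N/2 per arm, each with probability (1 − loss)·p. HR is 0.50.

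| Loss | N = 80, P(<40) | N = 80, P(36–39) | N = 100, P(<40) |
|---|---|---|---|
| 20% | 4.8% | 4% | 0.01% |
| 30% | 37% | 26% | 0.9% |
| 40% | 84% | 30% | 19% |

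If the true HR is 1.0, events come faster: at N = 80 and 20% loss, P(<40) is 0.03%.

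**4. What a tolerance would change.** Using the formula in step 1 with 36 events instead of 40, the chance of observing HR ≤ 0.60 when the truth is 0.50 moves from 71.8% to 70.8%. The chance of observing HR ≤ 0.75 when the truth is 1.0 moves from 18.1% to 19.4%. Deciding on 36 to 39 events is therefore nearly the same as deciding on 40.

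**5. What a loss percentage would have to be.** Expected events at month 35 equal 40 when loss = 1 − 40/(events without loss):

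- HR 0.50: 1 − 40/58.4 = 32% at N = 80; 1 − 40/73.1 = 45% at N = 100.
- HR 1.0: 1 − 40/67.8 = 41% at N = 80; 1 − 40/84.7 = 53% at N = 100.

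The threshold runs from 32% to 53%, and half of what determines it (the true HR) is unknown while the trial is blinded. The event-and-time limit already in Section 7.3 needs no such input.

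**6. The two readings side by side.** If the dropout phrase gives the expected cause, and the count and date are the trigger, any shortfall ends at 20 months and the loss measures do not conflict. The entries for Sections 7.3 and 7.7 under Global Amendment 4 (Section 11.4) support this: the change allows analysis without 40 events provided expansion is then ruled out, and the motive given is patients leaving before objective progression. If the phrase is a strict condition, a shortfall from central non-confirmation stays under the default rule and the analysis waits. Neither reading produces an invalid analysis.

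**The case for a change.** The strongest opposing case is that the literal text does separate cases that should be treated alike. Take N = 80 and 35% total loss at HR 0.50: expected events at month 35 are 0.65 × 58.4 = 38.0. If all the loss is dropout, the exception can cancel the look. If it is 15% dropout plus 20% central non-confirmation (an assumed split), the same 38 events can pass as approximately 40 and go to the DMC. Section 11.4 also records more early dropout than expected, so heavy loss was a live prospect, and a few sentences would remove the doubt at no cost in patients or alpha.

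The mismatch in wording stands, as does the absence of any rule for attributing a shortfall to one source. Three things limit it. The default paragraph itself uses a bare 40 for the planned count, and Section 7.7 does so for the expansion decision, so the exception can be read as the same target, projected in the same way. Raising N to 100, already allowed, cuts the 37% at 30% loss to 0.9%. And not every centrally unconfirmed progression is lost for good, since patients treated beyond progression continue imaging with central submission, so the flat-loss model overstates that route.

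**Conclusion.** No change is needed. The exception is loosely worded, but its trigger can be applied: 40 events out of reach, or not reached 20 months after last randomisation. It can only withhold seamless expansion, so it cannot inflate the type I error. All endpoints are still reported and a separate Phase III trial remains possible. The team and the DMC can settle sensibly whether 38 projected events count as about 40, and the operating characteristics differ by little more than one percentage point between 36 and 40 events. A loss percentage would be a debatable trade-off, because no single value suits both sample sizes and the range of true hazard ratios.

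At the planned 20% loss the limit is missed in about 5% of trials (N = 80, HR 0.50) and almost never at N = 100. The question becomes material from about 30% loss at N = 80. These figures assume exponential PFS, uniform accrual and flat loss. The DMC charter was not available and may say more. Section 1.4 of the Protocol reports the primary analysis as complete with no added benefit, so the rule no longer governs a decision.
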